4.2.2 Principal Secondary Outcome

Change in generic HRQOL from baseline to 12, 26 and 52 weeks as assessed using the EuroQol (EQ) 5D-5LTM and EQ Visual Analogue Score (VAS) (Appendix B-2). This short self-administered generic tool consists of a descriptive system with 5 questions in 5-point Likert-type format, which assess how significantly the domains of mobility, self-care, usual activities, pain/discomfort and anxiety/depression are affected in daily life. The EQ-5D-5L Index, based on health state valuations elicited from the general public ^{54,55}, is anchored at 0.0 (dead) and 1.0 (full health). A minimum increment of 0.03 in the EQ-5D-DL index score can be considered clinically important as it corresponds to the smallest coefficient for a change from 'No problem' to 'Some problems' within a dimension of the EQ-5D-DL. The EQ VAS asks individuals to rate their current state of health from "worst imaginable" to "best imaginable" on a 100-point scale. ⁵⁶ EQ-5D-5LTM is brief and has been extensively validated in various populations and disease states. Normative data for Canadians and ESKD exist. ^{11,57}

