9.2 Sample Size and Power

Based on the limited literature published in this area, we expect an absolute difference of 25% between the intervention and control groups in the proportion of individuals in whom DSI severity score decreases by 7 points or more over time.

We predict DSI score will decrease in 50% of the intervention group and 25% of the control group at 12weeks (baseline prevalence of symptoms assumed to be 50%). A sample size of 58 patients in each arm will allow us to detect this difference with 80% power (alpha 0.05). We conservatively anticipate 30% dropout.⁸³ Therefore, a target sample size of 150 participants (75 participants per study arm) is proposed.

This sample size will allow us to detect a 7-point difference in mean change in DSI severity score using standard deviation of 16 with 80% power and alpha 0.05. This sample size (n=75 in each arm) will also provide 80% power with 0.05 alpha to detect a 12-point difference between groups in mean change in HRQOL measured using EQ-VAS (considered clinically important difference in other chronic diseases)⁸⁵ and a 30% absolute difference in proportion of individuals endorsing deficits in each domain of EQ5D-3L over time assuming 50% baseline deficit and development of new deficits in an additional 10% of the control group and a reduction in deficits in 15% of the intervention group.

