9.3.3 Secondary Outcomes and Analyses

We will repeat the primary outcome analyses that compared change in DSI from baseline to 12 weeks between groups, instead looking at change from baseline to 26 weeks and 52 weeks.

Change in EQVAS over time will be compared between study groups using Student's T-test. As well, we will compare the difference in proportion of individuals who develop new deficits (score of 2 or 3) in each domain of the EQ5D-5L over time. The degree to which change in symptom burden correlates with change in EQVAS will be assessed using Spearman and Pearson's correlation coefficients as indicated based on distribution of the data. Change in all other secondary outcomes over time will be compared between groups using the appropriate parametric and non-parametric statistical tests depending on data type and distribution. Bonferroni adjustments will be made for secondary outcomes to adjust for multiple study timepoints. Hospitalization will be analyzed using Poisson regression. For all analyses, two-sided p < 0.01 will be statistically significant. Statistical analysis will be performed using SAS 9.3 (Carey, NC).

We will validate the Godin Shepard Leisure-Time Exercise Questionnaire using accelerometry data. Correlation between Godin Questionnaire Score and active minutes (light, moderate and moderate-vigorous activity) measured by accelerometry at each study assessment time point will be assessed using Pearson or Spearman correlation depending on distribution of the data. Internal consistency of the Godin questionnaire will be assessed using Cronbach alpha and Intraclass Correlation Coefficient. In those individuals in which active minutes measured using accelerometry did not change between assessment periods (change of less than 10% from baseline), test re-test reliability of the Godin Questionnaire will be assessed using Kappa statistic. Responsiveness will be modelled using linear regression with Godin questionnaire score as the primary predictor of active minutes measured by accelerometry. Additional predictors including sex, age, diabetes and other comorbidities will be added to the model as sample size will allow.

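### The 80% power stated for EQ-VAS in section 9.2 assumes alpha 0.05, but section 9.3.3 tests secondary outcomes under two stricter rules that are reconciled neither with each other nor with 9.2

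*Combined protocol and SAP*

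**What the plan says.** Section 4.2.2 names EQ-5D-5L and EQ-VAS together as the principal secondary outcome: "Change in generic HRQOL from baseline to 12, 26 and 52 weeks".

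After sizing the trial on the primary outcome, section 9.2 adds a power statement for EQ-VAS: "This sample size (n=75 in each arm) will also provide 80% power with 0.05 alpha" for a "12-point difference between groups in mean change in HRQOL measured using EQ-VAS". It gives no SD for EQ-VAS. The same section says: "We conservatively anticipate 30% dropout".

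Section 9.3.3 gives the analysis: "Change in EQVAS over time will be compared between study groups using Student's T-test". It then says: "Bonferroni adjustments will be made for secondary outcomes to adjust for multiple study timepoints". It names neither the alpha to be divided nor the number of comparisons to divide by. Two sentences later it sets a significance threshold of two-sided p below 0.01 for all analyses. It does not say whether 0.01 replaces the Bonferroni adjustment, is its result, or is the level to be adjusted.

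**The concern.** The power figure is calculated at a level that the analysis section does not use. EQ-VAS is a secondary outcome with three follow-up visits, and nothing exempts it from the Bonferroni rule. Even without that rule, the general 0.01 threshold would displace the 0.05 behind the 80%.

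Two things are at stake. A reader of 9.2 would believe that a true 12-point benefit has a 20% chance of being missed, whereas under the analysis rules and the SD implied by 9.2 that chance is about 35% or more. Also, because 9.3.3 allows at least three thresholds (0.05/3, 0.01 or 0.01/3), the verdict on EQ-VAS could depend on a choice made after the data are seen.

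**Working it through.** **Inputs.** Difference 12 points, 75 per arm, alpha 0.05 and power 80% (section 9.2); t-test between groups (9.3.3); three time points (4.2.2); dropout 30% (9.2). Assumed, because the documents do not say: the alpha in 9.2 is two-sided, and the Bonferroni divisor is 3, one for each follow-up visit.

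**Step 1: the plan's own figure.** The 80% cannot be checked independently without an SD. It can only be inverted to find the SD that makes it true:

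SD = 12 / [(1.960 + 0.842) × √(2/75)] = 26.2 (normal approximation).

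The same calculation with the noncentral t gives 26.1.

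**Step 2: the candidate thresholds.** 0.05/3 = 0.0167; 0.01; 0.01/3 = 0.0033. The two-sided critical values are z = 2.394, 2.576 and 2.935.

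**Step 3: power at 75 per arm.** If power is 80% at 0.05, the standardised effect is 1.960 + 0.842 = 2.802, and power at another alpha is Φ(2.802 − z). The SD cancels.

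- 0.05/3: Φ(2.802 − 2.394) = 65.8%
- 0.01: Φ(2.802 − 2.576) = 58.9%
- 0.01/3: Φ(2.802 − 2.935) = 44.7%

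The noncentral t gives slightly lower values, used in the table below.

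**Step 4: evaluable patients.** 75 × 0.70 = 52.5, taken as 52 per arm, with the same SD of 26.1.

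| Threshold | Power, 75 per arm | Difference detectable with 80% power, 75 per arm | Power, 52 per arm |
|---|---|---|---|
| 0.05 (as in 9.2) | 80% | 12.0 points | 64% |
| 0.05/3 | 65.5% | 13.9 points | 47% |
| 0.01 | 58.4% | 14.7 points | 40% |
| 0.01/3 | 43.8% | 16.3 points | 26% |

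**Step 5: sensitivity to the divisor.** Starting from 0.05, a divisor of 2 gives 71.2% and a divisor of 4 gives 61.9% (normal approximation, 75 per arm).

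**Step 6: sensitivity to the SD.** If the 80% is not taken as given, power depends on the true SD. Normal approximation, at 0.05 / 0.0167 / 0.01 / 0.0033:

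- SD 20, 75 per arm: 95.7% / 90.0% / 86.4% / 77.0%
- SD 20, 52 per arm: 86.4% / 74.7% / 68.6% / 54.9%
- SD 25, 75 per arm: 83.6% / 70.7% / 64.2% / 50.2%
- SD 30, 75 per arm: 68.8% / 52.2% / 45.0% / 31.4%

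**The case against.** The strongest reply is that no calculation in 9.2 has been shown to be wrong. The SD of 26 comes from assuming that the challenged statement is exactly right. With an SD of 20, power at 75 per arm would be 90.0% at 0.05/3 and 86.4% at 0.01. This stands. A reader might infer that the trial will in fact have less than 80% power for EQ-VAS; without an SD, the documents do not support that. What they support is narrower: if 80% holds at 0.05, it cannot also hold at any threshold that 9.3.3 could mean.

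A reader might also blame the Bonferroni sentence alone. The text does not support that either. The 0.01 threshold in the same section would by itself bring the figure to about 58%, so removing or clarifying the Bonferroni sentence would not restore the 80%. Equally, changing 0.01 to 0.05 would leave the Bonferroni loss in place. The two need to be settled together.

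The divisor of 3 is inferred, but divisors of 2 and 4 do not bring back 80%. It may be said that the 80% was meant for the 58 evaluable patients per arm on which the primary calculation rests. The text says 75; on the other reading the implied SD is 23.1, and power at 58 per arm falls to the same 65.8%, 58.9% and 44.7%.

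Finally, the trial is sized on the primary outcome, and a secondary outcome need not be powered at all. That is fair and limits the weight of the point. But the plan chose to state a power, and it should be the power of the test it specifies.

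**Conclusion.** This is an internal inconsistency in a stated power, and it should be corrected. It does not touch the primary result. Taking 80% at 0.05 as given (implied SD about 26, two-sided test, divisor 3), the EQ-VAS power with everyone evaluable is somewhere between 44% and 65%, depending on how 9.3.3 is read. With the plan's own dropout and the same SD, the range is 26% to 47%, and dropout alone already lowers the 0.05 figure to about 64%. For that reason a replacement such as 65% power or 13.9 points should not simply be written into 9.2: it assumes that all 75 per arm are evaluable and settles on one of several possible thresholds. The absolute figures depend on an SD that the documents do not give; the mismatch between the power statement and the test does not.

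**What to change.** In section 9.3.3, state one significance rule for secondary outcomes: the base alpha, the number of time points it is divided by, and how the result relates to the 0.01 threshold. In section 9.2, state the SD of EQ-VAS change with its source, and restate either the power for 12 points or the difference detectable with 80% power, at that alpha and on the number per arm expected to be evaluable after dropout. Settle this in the same edit as the wider conflict between 0.05 in 9.2 and 0.01 in 9.3.3, and before the outcome data are examined by arm.

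Naming week 12 as the only EQ-VAS comparison without time-point correction would also be possible, but that changes the multiplicity strategy rather than the wording. While the 0.01 threshold stands, it would still give about 58% at 75 per arm.

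The recommended change needs no extra patients. Its cost is a stated EQ-VAS figure that is probably less favourable than the present one.

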Study Endpoints Primary, Secondary and Mechanistic	Primary outcome: Change in symptom burden over time (12 weeks) as measured by Dialysis Symptom Index (DSI) severity score. Secondary outcomes: Change in generic health-related quality of life over time (12, 26, 52 weeks) as measured by EuroQol 5D-5L and EuroQol visual analogue scale Change in: modified symptom burden (modified DSI severity score); time for recovery post-HD; frailty status (Fried criteria); physical activity level (accelerometer and Godin-Shephard Leisure Time Physical Activity Questionnaire); exercise capacity (Incremental Shuttle Walk Test); self-

	efficacy for exercise (Self-Efficacy for Exercise Questionnaire; hospitalization rate (number hospital days admitted/patient year); all cause 1 year mortality
Brief Summary of Analysis	Sample size : The following assumptions were made: alpha 0.05; power 0.80; 30% dropout and 25% absolute difference in proportion of individuals in whom DSI severity score decreases by 7 points or more (minimal clinically important difference). Therefore, assuming a baseline symptom prevalence of 50% of individuals in each study group, 150 patients (75 in each arm) will be randomized and we will be able to detect a 25% reduction in the primary outcome.
	Primary analysis : Intention-to-treat, available-case basis, in the intervention versus control arm, using Chi-square test and logistic regression for categorical outcomes and t-tests/MannWhitney U for continuous outcomes.
	Secondary outcomes : Descriptive statistics, Kaplan Meier analysis, Poisson regression and linear mixed modeling and will be used as appropriate.

SCHEMATIC OF THE STUDY DESIGN

Enrolment and consent: Once informed consent is obtained, the Dialysis Symptom Index (DSI) will be administered to all participants. Those who score 0 on the DSI (no symptoms) will be deemed ineligible for the study

Randomization: To avoid bias, randomization will be performed following the baseline assessment.

Intervention phase: Participants in "intervention" group will receive study intervention during this time.

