4.2.3 Secondary Outcomes

Participation in an exercise rehabilitation program may have additional benefits for patients that are not captured by the above outcomes. Therefore, the following secondary outcomes will be evaluated:

- 1. Change in time required for recovery following hemodialysis (in minutes) from baseline to 12, 26, and 52 weeks. At each study assessment, participants will be asked to answer the question "Approximately how much time does it take to recover from a dialysis session". Answers will be recorded in minutes. Prolonged post-HD recovery time, defined as the answer to the question "How long does it take to recover from a dialysis session" has recently been identified as a troubling symptom complex and important outcome unique to individuals receiving HD.^{58, 59}
- 2. Change in symptom burden from baseline to 26 and 52 weeks as measured by the Dialysis Symptom Index (DSI) Severity Score (Appendix B-1). This will be measured as the proportion of individuals who have a decline of 7 points or more in symptom burden as defined by DSI symptom severity score from baseline to 26 and 52 weeks. The DSI is a 30-item self-administered questionnaire with low administrative burden developed to measure the presence (yes/no) and severity ("how much did it bother you" by 5 point Likert-scale ranging from "not at all" to "very much") of common emotional and physical symptoms over the previous week in individuals receiving maintenance HD.⁵¹ Symptom severity scores can range from 0 to 150. A 7-point change in severity score is likely to be clinically significant because this magnitude of change is: a) consistent with the resolution/addition of 1 "very bothersome" symptom plus a 1 point change in severity of 2 symptoms and likely to be significant to patients; and b) is approximately 1 standard error of the mean based on our pilot data (SD 30, n=18) and consistent with distribution-based methods. The DSI has been shown to be reliable in predicting HRQOL in multiple studies in North American and European HD populations.^{6,51-53}
- 3. Change in physical activity behaviour patterns from baseline to 12, 26 and 52 weeks assessed:

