- **6.** Change in self-efficacy for exercise from baseline to 12, 26 and 52 weeks assessed using the Self-Efficacy for Exercise Survey (Appendix B-4). This self-reported tool consists of 9 brief questions in 10-point Likert scale format. The summary score indicates an individual's perception of their ability to successfully incorporate physical activity into daily routine and is the strongest determinant of continued exercise participation following formal exercise or rehabilitation programs. This measure has reliably predicted physical activity behavior in elderly individuals from various cultural backgrounds. The summary score indicates an individual score in the summary score indicates an individual's perception of their ability to successfully incorporate physical activity into daily routine and is the strongest determinant of continued exercise participation following formal exercise or rehabilitation programs. This measure has reliably predicted physical activity behavior in elderly individuals from various cultural backgrounds.
- **7.** Hospitalization rate defined as the number of hospitalization days admitted per patient year. In addition, cause and length of any hospital stay for greater than 24 hours will be collected. At each study assessment time point, this will be determined by self-report and hemodialysis chart review.
- **8.** All-cause mortality defined as the proportion of patients who die over 1-year and cause of death obtained from dialysis unit records. Depending on number of events, analysis may be adjusted for time on dialysis, age and comorbidities.

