9.3 Description of Statistical Methods

9.3.1 Primary Outcome

Developed in consultation with a statistician ([name], Chronic Disease Innovation

Centre) familiar with RCTs and our study outcomes, analysis will be performed in an intention-to-treat manner on a case available basis. Change in DSI severity score from baseline to 12 weeks will be compared between groups by independent two-tailed t-test or Mann-Whitney U test depending on distribution and using generalized linear mixed models with study timepoint as a random effect and adjusted for baseline DSI score. In a subgroup of individuals whose baseline DSI score is >7, the proportion of individuals whose DSI severity score has improved by 7 or more points from baseline to 12 weeks will be compared between groups at each study time point using Chi-square test.

Multiple logistic regression will be performed to determine predictors of a >7 point change in DSI severity score over time and adjusted for time varying confounders using a marginal structural model. Interaction terms for sex and baseline DSI score will also be inputted into the model. Although study group will be the primary predictor in this model, other key predictors of symptom burden (including baseline DSI score, diabetes status, ischemic heart disease (IHD), age, gender, race, smoking status, serum albumin level, hemoglobin, baseline physical function, physical activity level and interaction terms for gender/intervention and baseline DSI score/intervention) will also be tested in a step-wise manner.

If **missing outcome data** is greater than anticipated (25%) we will impute them according to current FDA/NAS/NRC recommendations using multiple imputation with chained equations ⁸⁶⁻⁸⁸. Specifically, multiple imputation creates 20-40 complete datasets with plausible values from the model-based predictive distributions, and pooled estimates and standard errors are obtained through the use of Rubin's combining rules. These models are predicated on the assumption that the data are missing at random (MAR). Finally, the robustness of the inferences about treatment effects to violations of the MAR assumptions will be evaluated through a sensitivity analysis ⁸⁸.

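### The trial is sized at alpha 0.05, but the only significance threshold in the analysis section is p < 0.01 for all analyses; taken literally, primary power falls from 80% to about 58%

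*Combined protocol and SAP*

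**What the plan says.** **Sizing.** The synopsis (Brief Summary of Analysis) lists its assumptions as "alpha 0.05; power 0.80; 30% dropout and 25% absolute difference in proportion of individuals" with a DSI fall of at least 7 points. Section 9.2 expects 50% responders with the intervention and 25% with control, and says that 58 patients per arm "will allow us to detect this difference with 80% power (alpha 0.05". It then sets 75 per arm to allow for 30% dropout. For the secondary quality-of-life outcomes, 9.2 says that 75 per arm "will also provide 80% power with 0.05 alpha to detect a 12-point difference between groups" on the EQ-VAS, and makes a similar statement for the EQ-5D domains.

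**Primary analysis.** Section 9.3.1 begins: "Change in DSI severity score from baseline to 12 weeks will be compared between groups by independent two-tailed t-test", with a Mann-Whitney alternative. It adds mixed models, a chi-square test on the responder proportion and a logistic model. It gives no significance level for any of them.

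**Threshold.** Section 9.3.3 says: "Bonferroni adjustments will be made for secondary outcomes to adjust for multiple study timepoints". After one sentence on hospitalization comes: "For all analyses, two-sided p < 0.01 will be statistically significant".

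**The concern.** A sizing assumption and a decision rule should use the same alpha. Here the sizing uses 0.05 and the only written decision rule uses 0.01. A primary p-value between the two would be a success by 9.2 and a failure by 9.3.3 as worded, and no text says which governs. If the question is settled only once the result is known, either choice can be challenged as data-driven.

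The secondary rule is unclear too. The 0.01 could be the level before the Bonferroni step, the level after it, or a replacement for it. For an outcome tested at three time points, Bonferroni from 0.05 gives 0.05/3 = 0.0167, and from 0.01 it gives 0.01/3 = 0.0033. Neither is 0.01.

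**Working it through.** **Inputs.** From 9.2: p1 = 0.50, p2 = 0.25, 80% power, alpha 0.05, 58 evaluable and 75 randomized per arm, 30% dropout. From 9.3.3: two-sided 0.01. Section 9.2 does not state sidedness; I use two-sided, which reproduces its figure (one-sided gives 46).

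**1. Reproducing 58 per arm.** Pooled two-proportion formula, with p̄ = 0.375:

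n = [z(1−α/2)·√(2p̄(1−p̄)) + z(0.80)·√(p1(1−p1) + p2(1−p2))]² / (p1−p2)²

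The two roots are √0.46875 = 0.6847 and √0.4375 = 0.6614.

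- α = 0.05: (1.960 × 0.6847 + 0.8416 × 0.6614)² / 0.0625 = 57.7, so 58. This matches the plan.
- α = 0.01: (2.576 × 0.6847 + 0.8416 × 0.6614)² / 0.0625 = 86.1, so 87.

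**2. Power at each level.** Power = Φ{[0.25 − z(1−α/2)·0.6847/√n] / (0.6614/√n)}. At n = 58 the two standard errors are 0.0899 and 0.0869.

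- α = 0.05: (0.25 − 1.960 × 0.0899)/0.0869 = 0.850, power 80.2%.
- α = 0.01: (0.25 − 2.576 × 0.0899)/0.0869 = 0.212, power 58.4%.

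| Evaluable per arm | Power at 0.05 | Power at 0.01 |
|---|---|---|
| 52 (75 × 0.70 = 52.5) | 75.7% | 52.4% |
| 58 | 80.2% | 58.4% |
| 75 (no dropout) | 89.3% | 72.8% |

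The step from 80% to 76% in the 0.05 column is a separate shortfall in the dropout allowance (58/0.70 = 83, not 75) and has nothing to do with 0.01. Exact binomial power of the uncorrected chi-square at 58 per arm is 79.9% and 59.3%, so the drop is not an artefact of the approximation.

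**3. How often the two rules disagree.** At 58 per arm: 80.2% − 58.4% = 21.8%.

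**4. What that looks like in data.** Uncorrected chi-square, 58 per arm, 14 control responders (24%):

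| Intervention responders | p | At 0.05 | At 0.01 |
|---|---|---|---|
| 24 (41%) | 0.048 | pass | fail |
| 25 (43%) | 0.031 | pass | fail |
| 26 (45%) | 0.019 | pass | fail |
| 27 (47%) | 0.012 | pass | fail |
| 28 (48%) | 0.007 | pass | pass |

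**5. EQ-VAS.** Section 9.2 gives no SD. Accepting its 80% at 0.05 with 75 per arm fixes the t-test noncentrality at 2.82 on 148 df (implied SD 12 × √(75/2)/2.82 = 26.1). Power is then 58% at 0.01 and 65% at 0.0167, whatever the SD.

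**6. EQ-5D.** Section 9.2 states a 30-point difference, but its components give 50 + 10 = 60% versus 50 − 15 = 35%, which is 25 points. With the step 2 formula at 75 per arm, moving from 0.05 to 0.01 takes power from 87% to 69% for 60% versus 35%. For 60% versus 30%, my assumption for the 30-point reading, it goes from 97% to 88%.

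**The case against.** The strongest reply is placement. The sentence is under a secondary-outcomes heading, shortly after a Bonferroni rule limited to secondary outcomes, and every place that attaches an alpha to the primary says 0.05. On that reading the plan is ambiguous and loses no primary power. This is a fair account of what the authors may have meant, and the 58% is conditional on the literal reading. But the Bonferroni sentence names secondary outcomes while the threshold sentence, two sentences later, says all analyses. The sentence after it, on software, is plainly trial-wide. The secondary-only reading also still contradicts the 0.05 used in 9.2 for the EQ-VAS and EQ-5D. Part of that last mismatch would exist from the Bonferroni step alone.

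A second reply is that the 58% describes one test. Section 9.3.1 lists several analyses, starting with mean DSI change. For 7 points and SD 16, t-test power at 58 per arm is about 65% at 0.05 and 40% at 0.01; at 75 per arm it is about 76% and 53%. Section 9.3.1 also confines the chi-square to patients with baseline DSI above 7, so the number tested may be below 58. The EQ-5D figures likewise describe the proportions in 9.2, not the new-deficit comparison in 9.3.3. These limits on precision stand. They are separate problems and do not reconcile 0.05 with 0.01.

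A third reply is that the correction is only a few sentences and so the matter is minor. The cost is small, but the sentences decide whether the primary result counts as positive.

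**Conclusion.** The concern holds. The plan sizes the primary at 0.05, gives no level where the primary analysis is described, and states 0.01 for all analyses. Read literally, primary power at the stated 58 per arm is 58.4%, not 80%, and 87 evaluable per arm would be needed to restore 80%. On either reading of the sentence, part of 9.2 conflicts with 9.3.3. The primary figures assume 50% versus 25% responders, an uncorrected two-sided chi-square test and 58 patients per arm in that test. The EQ-VAS figures assume that the plan's own 80% claim is right.

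**What to change.** By dated amendment before unblinding:

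1. In 9.3.1, state that the 12-week primary comparison is tested at two-sided alpha 0.05, matching 9.2.
2. In 9.3.3, replace the all-analyses sentence with one explicit rule for secondary outcomes. Either of these would do:
   - Divide 0.05 by the number of time points tested for the outcome. That is three for the EQ-VAS, EQ-5D and other outcomes at 12, 26 and 52 weeks (0.0167), two for the item in 4.2.3 worded "Change in symptom burden from baseline to 26 and 52 weeks as measured by the Dialysis Symptom Index (DSI) Severity Score" (0.025), and one for one-year hospitalization and for "All-cause mortality defined as the proportion of patients who die over 1-year" (0.05).
   - Use a flat 0.01 and say that it replaces the Bonferroni step.
3. In 9.2, restate the EQ-VAS and EQ-5D power at the chosen level.

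If 0.01 is intended for the primary, say so in 9.3.1 and restate primary power as about 58% at 58 per arm (about 52% at 52 per arm).

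The cost is one sentence in 9.3.1, one or two in 9.3.3 and the restated power in 9.2. If 0.05 is confirmed for the primary, neither the sample size nor trial conduct changes.
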